13.8 Physical Examination

The number and percentage of subjects with normal and abnormal findings in the physical examination will be presented by body system, visit, and treatment group as defined in Section 5.

14 PHARMACOKINETICS ANALYSIS

A single PK draw will be performed at Week 24 (Cohort-Week 24) or Week 52 (Cohort-Week 52) for subjects ≥ 12 years of age at entry in parent study who originally enrolled into ARQ-151-313 under protocol amendment 1.

Concentration data will be summarized using descriptive and geometric statistics (refer to Section 5.6) by treatment group as defined in Section 5. For computation of mean plasma concentrations, data that are below the limit of quantification (BLQ) will be set to zero. The PK population will be used for these analyses.

PK data will be presented in the listing.

 Innovaderm Research 	STATISTICAL ANALYSIS PLAN, Final Version 1.0
Protocol Number: ARQ-151-313	Sponsor: Arcutis Biotherapeutics, Inc.

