4. INVESTIGATIONAL PLAN

4.1. Overall Study Design and Plan

This is a Phase 3, open-label, single-arm, long-term safety study in which ARQ-151 cream 0.15% or ARQ-151 cream 0.05% is applied QD x 24 (Cohort-Week 24) or 52 weeks to subjects with mild to moderate atopic dermatitis (except for time on BIW maintenance therapy).

- Eligible subjects will enroll into the long-term safety study on the same day as the Week 4 visit of the preceding study (ARQ-151-311 or ARQ-151-312 or ARQ-151-315).
- Subjects/caregivers will apply ARQ-151 cream 0.15% for subjects \geq 6 years old or ARQ-151 cream 0.05% for subjects 2-5 years old.
- If a 5 year-old subject turns 6 years-old during this study, the subject will be switched from ARQ-151 cream 0.05% to ARQ-151 cream 0.15% at his/her first scheduled post-birthday visit. Dose reduction back to 0.05% is not permitted.
- The study drug will be applied QD for 24 (Cohort-Week 24) or 52 weeks to all AD affected areas and any newly appearing AD lesions that arise during the study, except on the scalp (unless entering BIW maintenance therapy, as described below).
- **For the first 4 weeks of study ARQ-151-313, all subjects will apply study medication QD in the areas identified and treated as per the body diagram in the preceding study (ARQ-151-311/312/315).** Beginning at the Week 4 visit, any subject who achieves vIGA-AD of '0-clear' as confirmed by the Investigator at a scheduled or unscheduled clinic visit, will switch to twice weekly (BIW) maintenance treatment. For maintenance therapy, study medication will be applied on two nonconsecutive days per week (e.g. Monday and Thursday) to areas commonly and/or most recently affected by AD, and any areas where AD is developing. Subjects receiving maintenance treatment who experience AD worsening (signs and symptoms) for 1 week despite dosing twice weekly will phone the clinical study site, resume daily dosing, and complete the subject diary accordingly. The phone call (but not a clinic visit) is required to resume daily dosing. At clinic visits, subjects receiving maintenance treatment may continue twice weekly maintenance dosing if vIGA-AD is either '0-clear' or '1-almost clear'. Subjects will resume daily dosing if vIGA-AD \geq 2, and can resume daily dosing if signs/symptoms of AD are not adequately controlled with maintenance therapy despite vIGA-AD of '1-almost clear'.

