5.3.4. Pharmacokinetics Assessment

PK draws will be performed according to the Schedule of Visits and Assessments ([Section 1.3](#)) for all subjects at all sites under this Amendment 1:

- A single PK assessment (trough) will be performed in subjects ≥ 12 years old with a blood sample collected at Week 52/ET.
- No PK sample will be collected at Week 52/ET for subjects 2–11 years old.

Ensure study medication is not applied in the area where PK will be drawn.

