6.3. Subjects to Analyze

The safety populations are defined as all subjects who are enrolled and received at least one confirmed dose of study medication.

Pharmacokinetic Population (PK): The PK population includes all subjects receiving active drug and had a PK draw (concentration data available) post-baseline. This population will be used for the analysis of PK concentrations.

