^k A urine pregnancy test will be administered to all females of child-bearing potential. A negative result is required for continued participation in the study, and results must be available prior to dispensing of study drug at each visit.

^l For all subjects ≥12 years old entering this study under Amendment 1 a single PK trough draw will be collected at Week 52/ET for Cohort-Week 52 or Week 24/ET for Cohort 24 subjects. Ensure study medication was not applied in the area where PK will be drawn.

^m It is expected that kits will be dispensed based on %BSA affected and subject's age. Subjects who turn 6 years old during the study will switch to ARQ-151 cream 0.15% at their first scheduled post-birthday visit. See IP Handling Manual for details. Under Amendment 1, this is the final visit for Cohort-Week 24 and no kits will be dispensed at this visit.

ⁿ Dispensing of IP is allowed, if needed. Study site should review IP kit to ensure sufficient IP is available until the next visit and only dispense additional IP if needed. **All subjects will continue study medication application in the areas identified and treated as per the body diagram in the preceding study for the first 4 weeks of the current study (ARQ-151-313).**

^o Beginning at the Week 4 visit, any subject who achieves vIGA-AD of '0-clear' as confirmed by the Investigator at a scheduled or unscheduled clinic visit, will switch to twice weekly (BIW) maintenance treatment. For maintenance therapy, study medication will be applied on two nonconsecutive days per week (e.g. Monday and Thursday) to areas commonly and/or most recently affected by AD, and any areas where AD is developing. Subjects receiving maintenance treatment who experience AD worsening (signs and symptoms) for 1 week despite dosing twice weekly will phone the clinical study site, resume daily dosing, and complete the subject diary accordingly. The phone call (but not a clinic visit) is required to resume daily dosing. At clinic visits, subjects receiving maintenance treatment may continue twice weekly maintenance dosing if vIGA-AD is either '0-clear' or '1-almost clear'. Subjects will resume daily dosing if vIGA-AD ≥2, and can resume daily dosing if signs/symptoms of AD are not adequately controlled with maintenance therapy despite vIGA-AD of '1-almost clear'. Under Amendment 1, maintenance dosing determination will not be conducted at Week 24 for Cohort-Week 24.

STATISTICAL ANALYSIS PLAN, Final Version 1.0	

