4.3 Pharmacokinetic Population (PK)

The PK population includes all subjects who had a PK draw (concentration data available) post-baseline. This population will be used for the analysis of PK concentrations.

Of note, PK is only to be drawn on subjects aged 12 years or older who first enrolled under protocol amendment 1.

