5 GENERAL CONSIDERATIONS

Formats and layouts of tables, listings, and figures (TLFs) will be provided in a separate document (output general layout is described in [Appendix 1](#)).

For analysis purposes, the TLFs will be summarized overall and by previous treatment group in the parent studies as indicated below. Rollovers from the ARQ-151-311/312 studies will be summarized separately from rollovers from the ARQ-151-315 study.

- Rollovers from ARQ-151-311/312 studies
 - Roflumilast cream 0.15%
 - Vehicle / Roflumilast cream 0.15%
 - Pooled Roflumilast cream 0.15%
- Rollovers from ARQ-151-315 study
 - Roflumilast cream 0.05% or 0.15%
 - Vehicle / Roflumilast cream 0.05% or 0.15%
 - Pooled Roflumilast cream 0.05% or 0.15%

 Innovaderm Research	STATISTICAL ANALYSIS PLAN, Final Version 1.0
Protocol Number: ARQ-151-313	Sponsor: Arcutis Biotherapeutics, Inc.

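### The single PK trough is summarised only by parent-study arm, pooling daily, twice-weekly and possibly off-drug samples, so the result is hard to interpret

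*SAP*

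**What the plan says.** **Objective.** SAP 2 asks for the systemic exposure to roflumilast and its N-oxide. It is not tied to a dosing regimen.

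**Sampling.** Protocol 5.3.4: "A single PK assessment (trough) will be performed in subjects" aged 12 or over. The PK footnote in SAP 3.3 says that "a single PK trough draw will be collected at Week 52/ET for Cohort-Week 52 or Week 24/ET for Cohort 24 subjects". Protocol 5.5 repeats the Week 52 procedures at early termination (ET). SAP 14's own text names only Week 24 or Week 52.

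**Grouping.** SAP 14: "Concentration data will be summarized using descriptive and geometric statistics (refer to Section 5.6) by treatment group as defined in Section 5". SAP 5 defines those groups: "the TLFs will be summarized overall and by previous treatment group in the parent studies as indicated below". SAP 6.6 plans no PK subgroup. The only other PK output is a listing of unspecified content.

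**Population.** Protocol 6.3: "The PK population includes all subjects receiving active drug and had a PK draw (concentration data available) post-baseline". SAP 4.3: "The PK population includes all subjects who had a PK draw (concentration data available) post-baseline".

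**Regimen.** Under Protocol 4.1, from the Week 4 visit a subject who reaches vIGA-AD 0 moves from daily (QD) to twice-weekly (BIW) application on non-adjacent days, with Monday and Thursday as the example. The subject may later return to daily dosing.

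**BLQ.** For means, SAP 14 says that "data that are below the limit of quantification (BLQ) will be set to zero". SAP 5.6 also requires a geometric mean and geometric CV for PK, with no BLQ rule for them.

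**The concern.** One sample per subject is the study's only measurement of systemic exposure. The cell it is reported in is defined by what the subject received in a four-week study that ended 24 or 52 weeks before the scheduled draw. Within that cell the word trough covers a sample about one day after an application (QD), a sample three or four days after one (BIW on the Monday/Thursday example), and possibly a sample from someone who has stopped.

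A low pooled value could mean that little drug is absorbed or that many subjects were dosing infrequently. The planned table cannot tell these apart. That matters because Protocol 2.3.2 reports weight loss and psychiatric events with the oral drug, and because the primary safety objective (Protocol 3.1.1) is worded in terms of once-daily treatment, so readers will be inclined to take the PK table as exposure under daily use.

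**Working it through.** The documents give no expected concentration, LLOQ, half-life, BIW share or PK sample size. There is no plan figure to reproduce, and every numerical input below except the 2/7 dosing ratio is an assumption.

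**1. Does the grouping separate exposure?** PK is drawn only at age 12 or over. The 0.05% cream is for ages 2 to 5, so all PK subjects are ARQ-151-311/312 roll-overs on 0.15%. At a Week 24 or Week 52 draw, both parent arms have used the same cream for that long. What differs between subjects is current regimen and time since last application, and neither is in the table.

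**2. Can off-drug samples enter?** The SAP 3.3 footnote and Protocol 5.5 put a draw at early termination, while SAP 14 does not mention one. The SAP PK population needs only a post-baseline concentration. The protocol's version also requires receipt of active drug but does not say when, and in a single-arm study nearly everyone meets that. Inclusion is possible, but it is not stated.

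**3. Effect on the arithmetic mean.** Let pB and pS be the shares on BIW and already stopped, and rB the BIW concentration relative to QD. Stopped subjects are taken as zero.

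Pooled mean / QD mean = (1 − pB − pS) + pB × rB

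With rB = 2/7 (two applications a week against seven; linear PK and equal treated area assumed):

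| pB | pS = 0 | pS = 5% |
|---|---|---|
| 10% | 1 − 0.10 × 5/7 = 0.929 | 0.879 |
| 30% | 1 − 0.30 × 5/7 = 0.786 | 0.736 |
| 50% | 1 − 0.50 × 5/7 = 0.643 | 0.593 |

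Letting rB run from 0 to 1 and pS from 0 to 10%, the ratio is 0.80 to 1.00 at pB = 10% and 0.30 to 1.00 at pB = 60%.

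**4. Troughs rather than averages.** The ratio 2/7 is an average-exposure ratio, but the sample is a trough. One-compartment superposition with k = ln 2 / half-life gives:

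- QD trough: e^(−k) / (1 − e^(−k))
- BIW, 3 days after Monday: (e^(−3k) + e^(−7k)) / (1 − e^(−7k))
- BIW, 4 days after Thursday: (e^(−4k) + e^(−7k)) / (1 − e^(−7k))

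At a 1-day half-life the QD value is 0.5/0.5 = 1. The BIW values are (0.1250 + 0.0078)/0.9922 = 0.134 and (0.0625 + 0.0078)/0.9922 = 0.071. At 4 days the BIW/QD ratios are 0.240 and 0.215. For half-lives from 0.5 to 7 days, rB is 0.05 to 0.26 at three days and 0.01 to 0.24 at four. If the sample is taken one day after the Monday application, rB is 0.32 to 0.75.

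At pB = 30% and pS = 0, rB = 0.071 gives 1 − 0.30 × 0.929 = 0.721, and rB = 0.240 gives 1 − 0.30 × 0.760 = 0.772.

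**5. BLQ.** Log-normal simulation: CV 80% or 150%, LLOQ 0.1 or 0.3 of the QD median, rB 2/7 or 0.10, pB 30% or 50%, pS 5%.

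- Setting BLQ to zero, applied to QD subjects alone, left the mean at 0.986 to 1.000 of its true value.
- The pooled median, with BLQ as zero, was 0.00 to 0.67 of the QD median.
- The geometric mean is undefined with any zero. With zeros dropped it was 0.54 to 1.23 of the true QD geometric mean.

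**The case against.** The strongest case against is that nothing is biased relative to the stated target. The PK objective is not limited to daily dosing, and switching to BIW is part of the regimen studied. A mean over everyone sampled is a fair description of exposure as the cream was used. If that mean falls as more subjects clear, their exposure has really fallen. PK is not a protocol primary or secondary endpoint, the analysis is descriptive, quartiles and maxima are reported, and the data are listed. Protocol 2.3.1.3 and 2.3.1.4 describe separate PK studies with daily application, including maximal use. All of this stands.

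It follows that a reader might infer that the reported exposure understates exposure under daily use. The documents do not support that as a general statement. SAP 14 never presents the figure as a daily-use value. The geometric mean may be undefined or too high. The size depends on quantities not given, and the zero rule for BLQ contributes little to the mean. Nor do the documents show that off-drug samples will enter in any number.

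A split by regimen has its own selection problem. BIW subjects are those who cleared, and QD subjects also treat active lesions (Protocol 4.7.3), so regimen is confounded with disease extent and treated area.

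What the objection does not answer is that parent arm is uninformative for this endpoint. The SAP itself treats regimen as important elsewhere: it derives BIW intervals (SAP 5.5), tabulates time on BIW and applies separate QD and BIW compliance limits (SAP 11).

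**Conclusion.** The point holds as a gap in interpretability. The only planned PK grouping does not separate exposure, and the factor most likely to do so is left out. The pooled arithmetic mean and median describe exposure as used. They would be lower than under daily dosing to the extent that BIW or off-drug troughs are lower, which 2/7 of the application frequency makes likely but does not prove. The size is not fixed by the documents: the ratios above rest on assumed regimen shares, half-lives, linear PK and equal treated area, and across the full range tried they run from 0.30 to 1.00.

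Two parts need no numerical assumption: the SAP and protocol passages on ET samples and the PK population do not match, and the geometric statistics have no workable BLQ rule. The importance is moderate and the remedy is cheap.

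**What to change.** In SAP 14:

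1. Keep the overall summary and add a descriptive one by regimen at the draw (QD, BIW, off drug), showing time since last application. Protocol 4.7.4 has the diary record the date and time of each dose.
2. Reconcile Protocol 6.3 with SAP 4.3 on the PK population, and the SAP 3.3 footnote with SAP 14 on ET draws. List or summarise off-treatment samples separately. If the wider SAP population is intended, record it as a change in SAP 3.6.
3. Report n (%) BLQ, and state a rule for the geometric statistics: either a non-zero substitution or quantifiable samples only.
4. State that the split is descriptive and that the QD stratum is not an estimate of population exposure under daily use.

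The cost is SAP wording and one extra table, with smaller cells. One check is needed: SAP 11 works from applied and missed dose counts in the eCRF, so confirm that the last application date and time before the draw reach the database, and enter them for PK subjects if they do not. No visit, sample or treatment rule changes.

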16 APPENDICES

Appendix 1

Output Conventions

TLF will be generated using SAS® and will be displayed on letter size paper with landscape orientation, 1-inch margins and 9 pt. Courier New font.

The header section will comprise the sponsor's name, the protocol number, the delivery description, the data cut-off date (if applicable), the TLF number, the TLF title, the analysis set, and the page number (Page X of Y). The footer section will include the TLF footnotes, the CRO's name, the date and time of the execution of the program, and the name of the program.

The mean, median, geometric mean will be displayed to one more decimal place than the original value; Q1, Q3, minimum and maximum will keep the same number of decimal places as the original value; standard deviation, standard error, CV and CI will be displayed to two more decimal places than the original value. If derived parameters are to be summarized, the number of decimals of the derived values is to be chosen on a case-by-case basis, but the rule above applies.

For categorical summary tables, percentages will be reported to one decimal place. Percentages between 0 and 0.1 (both exclusive) will be displayed as “<0.1”. The denominator for each percentage will be the number of subjects within the population per treatment group unless otherwise specified.

Listings will be ordered by treatment received in parent study and this study, subject number, date and visit (where applicable). Imputed dates will not be presented in the listings.

Dates & Times Format

Date and time (if available) will be presented in the format yyyy-mm-dd/hh:mm.

 Innovaderm Research	STATISTICAL ANALYSIS PLAN, Final Version 1.0
Protocol Number: ARQ-151-313	Sponsor: Arcutis Biotherapeutics, Inc.

Presentation of Treatment Groups

When applicable, study treatments will be represented as follows in the different outputs:

For summary tables:

Parent Study Treatment Full Name	Study Treatment Output Name	Notes:
Roflumilast cream 0.15%	Roflumilast cream 0.15%	ARQ-151-311/312 roll-overs
Vehicle	Vehicle / Roflumilast cream 0.15%	ARQ-151-311/312 roll-overs
n/a	Pooled Roflumilast cream 0.15%	ARQ-151-311/312 roll-overs
Roflumilast cream 0.05%	Roflumilast Cream 0.05% or 0.15%	ARQ-151-315 roll-overs
Vehicle	Vehicle / Roflumilast cream 0.05% or 0.15%	ARQ-151-315 roll-overs
n/a	Pooled Roflumilast cream 0.05% or 0.15%	ARQ-151-315 roll-overs

For listings and figures:

Parent Study Treatment Full Name	Study Treatment Output Name	Notes:
Roflumilast cream 0.15%	Roflumilast cream 0.15%	ARQ-151-311/312 roll-overs
Vehicle	Vehicle / Roflumilast cream 0.15%	ARQ-151-311/312 roll-overs
Roflumilast cream 0.05%	Roflumilast Cream 0.05% or 0.15%	ARQ-151-315 roll-overs
Vehicle	Vehicle / Roflumilast cream 0.05% or 0.15%	ARQ-151-315 roll-overs

 Innovaderm Research ■■■	STATISTICAL ANALYSIS PLAN, Final Version 1.0
Protocol Number: ARQ-151-313	Sponsor: Arcutis Biotherapeutics, Inc.

Appendix 2

Algorithm for Imputation of Start/End Date and Time of Adverse Events and Prior/Concomitant Medications

Event Start Date Imputation

- Imputation of event end date should be done before imputation of event start date.
- Completely missing: Impute to the first study treatment date.
- Missing day and month: Impute to January 1st, unless year is the same as year of first study treatment dose date then impute to the first study treatment date.
- Missing day: Impute to the 1st of the month, unless month and year are the same as month and year of first study treatment dose date then impute to the first study treatment date.
- If imputed event start date is after event end date (imputed or not), set the event start date to the imputed event end date.

Event Start Time Imputation (for Adverse Events only)

- Imputation of event end time should be done before imputation of event start date.
- If the event start date is not the same as the first dose date or time part of the first dose date is missing, impute to 00:00.
- If the event start date is the same as the first dose date, impute to time part of first dose date.
- If the event start date is equal to event end date and imputed event start time is after event end time (imputed or not), set the event start time to the imputed event end time.

Event End Date Imputation

- Completely missing (and not flagged as “ongoing”): Impute to the last contact date.
- Missing day and month: Impute to December 31st, unless year is the same as last contact date then impute to the last contact date.
- Missing day: Impute to the last day of the month, unless year and month are the same as year and month of last contact date then impute to the last contact date.

Event End Time Imputation (for Adverse Events only)

- If the event end date is not the same as the last contact date or time part of the last contact date is missing, impute to 23:59.
- If the event end date is the same as the last contact date, impute to time part of last contact date.
